13.2 Appendix: Assessment & Management of Potential Acute Liver Injury

In the event a subject develops $ALT > 2 \times ULN$, the study site will make every reasonable attempt to have the subject return to the clinic within 24 hours and conduct the following investigations:

Repeat liver function tests

Hepatitis A IgM

Hepatitis B surface antigen and hepatitis B core IgM

Hepatitis C RNA.

Cytomegalovirus IgM

Epstein-Barr viral capsid antigen IgM (if unavailable, obtain heterophile antibody or monospot testing)

Hepatitis E IgM

Serum creatine phosphokinase (CPK) and lactate dehydrogenase (LDH)

Measure direct bilirubin if total bilirubin $\geq 2 \times ULN$

Measure INR

Full blood count including differential white cell count for eosinophilia

Anti-nuclear antibody, anti-smooth muscle antibody, and Type 1 anti-liver kidney microsomal antibodies

Liver imaging (magnetic resonance) to evaluate liver disease

If acetaminophen is a potential contributor, measure serum acetaminophen adduct HPLC assay if available locally

Record the appearance or worsening of clinical symptoms of hepatitis (jaundice, fatigue, nausea, vomiting, right upper quadrant pain or tenderness, fever, rash or eosinophilia) on the Adverse Events eCRF.

Record use of concomitant medications, acetaminophen, herbal remedies, other-over-the-counter medications, or putative hepatotoxins on the Concomitant Medications eCRF.

Record alcohol use.

Monitor subjects at least weekly until liver chemistries (ALT, AST, alkaline phosphatase, total and direct bilirubin) resolve, stabilize, or return to within baseline values.

6.10.2.3.	Urinalysis	21
6.10.2.4.	Coagulation	21
6.10.2.5.	Other Laboratory Assessments	22
6.10.3.	Electrocardiogram	22
6.10.4.	Vital Sign Measurements	22
6.10.5.	Physical Examination	22
6.11.	OTHER SAFETY DATA	23
7.	REFERENCES	23
8.	APPENDICES	24
8.1.	SCHEDULE OF STUDY PROCEDURES (NOTE: UNLESS SPECIFIED, ALL PROCEDURES LISTED BELOW ARE TO BE PERFORMED FOR BOTH PART A AND PART B)	24

List of Abbreviations

ADVM-043	AAVrh.10 vector expressing human A1AT
AE	adverse event
AST	aspartate aminotransferase
BAL	bronchial alveolar lavage
CBC	complete blood count
BEVS	baculovirus expressions vector system
cDNA	complementary DNA
CFR	Code of Federal Regulations
CTCAE	Common Terminology Criteria for Adverse Events
COPD	chronic obstructive pulmonary disease
DLT	dose-limiting toxicity
DMC	Data Monitoring Committee
ECG	electrocardiogram
eCRF	electronic case report form
ELF	epithelial lining fluid
ELISA	enzyme-linked immunosorbent assay
EOS	end-of-study visit
GCP	Good Clinical Practice
HIV	human immunodeficiency virus
ICF	informed consent form
ICH	International Council for Harmonisation
IEF	isoelectric focusing
IMP	investigational medicinal product
IND	Investigational New Drug Application
IRB	institutional review board
IV	intravenous
MedDRA	Medical Dictionary for Regulatory Activities
MTD	maximum tolerated dose
NE	neutrophil elastase
NOAEL	no-observed-adverse-effect level
PAT	protein augmentation therapy
PBMC	peripheral blood mononuclear cell
PE	physical examination
█	█
PI	Principal Investigator
SAE	serious adverse event
TEAE	treatment-emergent adverse event
TLC	total lung capacity
ULN	upper limit of normal
vg	vector genomes
WBC	white blood cell

1. Revision History

Version Number	Version Date	Author	Description of Significant Changes from Previous Approved Version
4.0	04-Sep-2019	[REDACTED]	Updated to reflect [REDACTED] and updates from Amendment 7. None of the previous versions were finalized.

2. Introduction

Study ADVM-043-01 is a Phase 1/2 study being conducted to test the safety and efficacy of ADVM-043 in subjects with alpha-1 antitrypsin (A1AT) deficiency. These subjects possess a mutation in the human A1AT gene that affects the production and normal functioning of A1AT protein. A1AT has been found to be most active in the lung, where it balances the activity of neutrophil elastase, an enzyme released in the setting of inflammation or infection. Unchecked enzymatic activity can lead to destruction of lung tissue and insufficient anti-neutrophil elastase activity, resulting in early-onset emphysema. A1AT deficiency resulting in 5-fold or greater decreases in plasma A1AT levels is associated with a greater risk for developing emphysema, chronic obstructive pulmonary disease (COPD), bronchiectasis, and asthma.

ADVM-043 will be administered by 2 routes: in Part A, a single dose in each of 4 cohorts will be administered by intravenous (IV) infusion. Based on the safety and efficacy data from Part A, the study may proceed to Part B. In part B of the study, ADVM-043 will be administered by intrapleural injection. The successful completion of this study will provide critical safety and preliminary efficacy data to determine whether to proceed to a Phase 3 pivotal study.

This statistical analysis plan (SAP) is based on the clinical study protocol ADVM-043-01 Protocol Amendment 7 dated 30 October 2018 and its associated electronic case report forms (eCRFs). This document describes the rules to be used in the analysis and representation of safety and efficacy data as presented in the clinical protocol.

3. Objectives

3.1. Primary Objectives

- *To assess the safety of ADVM-043 following IV administration*

3.2. Secondary Objectives

- *To assess the effect of ADVM-043 on plasma A1AT concentrations following IV administration [up to 52 weeks]*
- *To assess the safety and effect of ADVM-043 following intrapleural administration**

**Safety and efficacy data, including maximum tolerated dose (MTD), from Part A will be considered when determining whether to proceed to Part B.*

Based on the safety and efficacy data from Part A, and in consultation with the Study Principal Investigators, the study did not proceed to Part B and will be excluded from all the analyses.

4. Investigational Plan

4.1. Overall Study Design and Plan

Study ADVM-043-01 is a Phase 1/2, open-label, multicenter, dose-escalation, first-in-human study to evaluate the safety and efficacy of ADVM-043 (AAVrh.10 vector expressing human A1AT), an investigational medicinal product (IMP) that is intended to deliver a functional gene to the liver of the subjects with A1AT deficiency.

The study is intended to test the hypothesis that ADVM-043 to individuals with A1AT deficiency is safe and results in persistent potentially therapeutic levels of A1AT in blood and alveolar epithelial-lining fluid (ELF). Subjects enrolled in the study will be treatment-naïve to protein augmentation therapy (PAT) or will have stopped receiving PAT at least 8 weeks prior to treatment administration. Therefore, detection of plasma A1AT levels over baseline will provide evidence of activity of ADVM-043.

In Part A of the study, ADVM-043 will be administered by IV infusion up to 4 dose-level cohorts. In each cohort, ADVM-043 will be initially administered to 2 subjects and may be administered to an additional 3 subjects in each cohort level after review by a data monitoring committee (DMC). Safety and efficacy data, including the maximum tolerated dose (MTD) observed from Part A, will be considered when determining whether to proceed to Part B and at what dose level.

In Part A, the first subject assigned to a cohort will receive a single IV infusion of ADVM-043 at 8×10^{13} vg. Beginning on the day of treatment (Day 0), the subject will be monitored for safety and treatment effects at protocol-specified study visits (Appendix 13.1). The first subject will be considered a sentinel subject and a minimum of 2 weeks (14 days) will separate dosing of the first and second subjects within a cohort. There will be a minimum of 4 weeks between dosing of the last subject in one cohort and the first subject in the next cohort which will include a DMC review of the safety and efficacy data within a dosing cohort.

In Part B of the study, ADVM-043 will be administered by intrapleural injection at 1 dose-level. The Schedule of Assessments is in Appendix 13.1.

4.2. Study Endpoints

4.2.1 Safety Endpoints

Type, frequency, severity, duration, and relationship to study drug of any AEs and laboratory abnormalities graded according to the National Cancer Institute Common Terminology Criteria for Adverse Events (CTCAE) version 4.03.

4.2.2 Efficacy Endpoints

- *Changes in plasma concentrations of M-specific A1AT [up to 52 weeks]*
- *Changes in total plasma concentrations of A1AT [up to 52 weeks]*

[REDACTED]

Based on the safety and efficacy data from Part A, and in consultation with the Study Principal Investigators, the study did not proceed to Part B and will be excluded from all the analyses.

4.3. Definition of Dose limiting toxicity

The first subject dosed will be considered the sentinel subject. The proposed dosing interval is at least 14 days between the first (sentinel) subject and the second subject dosed within a cohort provided there are no safety concerns in the sentinel subject.

A dose-limiting toxicity (DLT) is defined as any AE with severity Grade ≥ 3 attributed to ADVM-043 and that occurs within the DLT observation period. The DLT observation period is based on data from ongoing studies in liver-targeting gene therapy showing that treatment-related AEs have occurred in general within 4 weeks of study treatment and have not led to long term sequelae.

The DLT observation period for the sentinel subject will be 6 weeks (14 days plus 4 weeks) post-study treatment and for the second or any subsequent subject within the same dosing cohort, 4 weeks post-study treatment. The DLT observation period will occur during the DMC and Adverum's review

period, during which decisions will be made to dose escalate to the next cohort, or to further expand an ongoing dose cohort.

Within each dosing cohort, the first DLT will result in cohort expansion from a total of 2 subjects to a total of 5 subjects. If more than one DLT occurs within the same dose cohort, the maximum tolerated dose (MTD) will have been exceeded; de-escalation and cohort expansion of the prior cohort or an additional intermediate dose may be considered. The MTD will be the dose at which no more than 1 of the 5 subjects in an expanded cohort experiences a DLT.

If no DLTs are observed within the 2 subjects dosed, dose-escalation can proceed, and the Sponsor may also elect to expand the cohort to further evaluate safety or efficacy endpoints.

If only 1 DLT occurs in a total of 5 subjects within a dosing cohort, the DMC and the Sponsor will review all safety data and recommend dose-escalation or progression to Part B.

Enrollment will be suspended pending adjudication by the DMC if, at any time during the study, any of the following occur:

- *Any Grade 4 or 5 AE, regardless of attribution*
- *Any Grade 3 AE attributed to ADVM-043*
- *Evidence of acute liver injury ($ALT > 5 \times ULN$)*

5. General Statistical Considerations

The study is a Phase 1/2 safety and preliminary measure of efficacy study. As a Phase 1 safety study, no formal statistical analysis is required. Descriptive and exploratory analyses will be performed on all data collected in this study to gain further insight into the efficacy and safety of this gene transfer therapy.

Statistical analysis will be performed using SAS software Version 9.4 or later. Continuous variables will be summarized using the mean, standard deviation, median, minimum value, and maximum value. Categorical variables will be summarized using frequency counts and percentages. All data will be provided in by-subject data listings.

Decimal rules for categorical summaries:

When count data are presented, the percent will be suppressed when the count is zero in order to draw attention to the non-zero counts. A row denoted "Missing" will be included in count tabulations where necessary to account for dropouts and missing values. The denominator for all percentages will be the number of subjects in that cohort within the population of interest, unless otherwise stated. Non-zero percentages will be rounded to one decimal place, except 100%, which will be displayed without any decimal places.

Decimal rules for continuous summaries:

- If the original value has decimal places 2 or less: mean and median will have one additional decimal place and SD will have 2 additional decimal places
- If the original value has 3 or more decimal places: mean, median and SD will all have 3 decimal places

Minimum and maximum will always have the same decimal places as the original measure, up to a maximum of 3 decimal places.

5.1. Sample Size

Formal sample size calculations were not performed. The total number will range between 2 and 25 subjects with 2-5 subjects per cohort. The initial cohort size of 2 was chosen because:

- It minimizes the number of subjects potentially exposed to a sub-therapeutic dose of ADVM-043, which has limited potential for a second administration due to the development of neutralizing antibodies.
- A1AT deficiency is a rare disease (prevalence of approximately 1 to 5 per 10,000); this small number of potential subjects will further be limited by the protocol exclusion criteria such as the presence of pre-existing neutralizing antibodies to AAVrh.10 and the requirement for the 8-week washout period for subjects on PAT before treatment with ADVM-043.
- Data from historical clinical trials show a low rate of withdrawal which further supports the initial cohort size of 2 because the likelihood of incomplete data is predicted to be low.

If a subject withdraws prior to completion of the DLT observation window, the subject will be replaced and followed for DLTs before decisions regarding cohort expansion are made.

5.2. Randomization, Stratification, and Blinding

This is an open-label study, so randomization and blinding are not applicable.

5.3. Analysis Set

Enrolled set will consist of all subjects who were dosed.

The full analysis set (FAS) will consist of all subjects who receive any amount of ADVM-043.

The FAS will be used for presenting demographics, baseline characteristics, efficacy, and overall safety and tolerability assessments. Assessments will be presented by cohorts and total.

5.4. Analysis Variables

All the data conventions below are applicable only for summaries. Listings will be as reported in CRF unless stated otherwise.

5.4.1. Study Visit and Window

Screening procedures are to be completed a maximum of 3 months prior to ADVM-043 administration (Day 0). Screening assessments may be performed on multiple days. Subjects may be re-screened upon consultation with Adverum. The Screening visit is defined as ≤ 3 Month before Day 0. The Baseline visit is defined as prior to study treatment (within 36 hours of study administration) on Day 0. (Schedule of Assessments is in Appendix 13.1).

5.4.2. Data Handling

All available efficacy and safety data will be included in data listings and tabulations as stated in [section 6](#).

In general, missing data will be treated as missing and no data imputation will be applied, unless otherwise specified.

5.4.3. Protocol deviations

A significant deviation is defined as a protocol deviation that affects primary efficacy assessments, the safety of a subject or the scientific value of the trial ('Study Deviation Manual'). Significant deviations can include nonadherence to entry criteria; enrollment of the subject without prior Sponsor approval; or nonadherence to FDA regulations or ICH GCP guidelines. Protocol deviations will be reviewed prior to database lock to determine if significant, and all significant deviations will be flagged.

5.4.4. Age

Age will be derived as follows:

Age (in years) = (Informed Consent date – Birthdate)/365.25

5.4.5. Medication flags

If a medication started and ended before Day 0 ([REDACTED] as directed by protocol) then, it is considered as prior medication;

If the start date is missing and the end date is before Day 0 then, it is prior medication;

If the start date is before Day 0 and the end date is on Day 0 then, it is prior medication;

If the start date is before Day 0 and the end date is after Day 0 then, it is concomitant medication;

If the start date is before Day 0 and the end date is missing then, it is concomitant medication;

If both the start and end dates are missing then, it is concomitant medication;

If the start date is missing and end date is after Day 0 then, it is concomitant medication;

If both start and end dates are on or after Day 0 then, it is concomitant medication;

Medications for which missing start and/or stop dates make it impossible to determine the prior or concomitant status, will be classified as concomitant medications;

████████████████████ concomitant medication, which are to be started on Day -1 prior to administration of ADVM-043.

5.4.6. DLCO Calculation

The DLCO data are collected at the local lab for each site, so results may be collected in domestic or SI units. The DLCO results in domestic units (mL/min/mmHg) will be converted to SI units (mmol/min/kPa) prior to analysis using the following conversion factor:

DLCO in SI units = (DLCO in domestic units) / 2.986

5.4.7. Adverse Event Flags

TEAE Flag: A treatment-emergent adverse event (TEAE) is any event that was not present before exposure to the IMP or any event already present that worsens in either intensity or frequency after exposure to the IMP. All AEs that started on/after Day 0 will be flagged as 'TEAE'.

DLT Flag: A dose-limiting toxicity (DLT) is defined as any AE Grade ≥ 3 attributed to ADVM-043 and occurring within the DLT observation period. The DLT observation period for the sentinel subject is 6 weeks (14 days plus 4 weeks) post study treatment; and for the second or any subsequent subject within the same dosing cohort, 4 weeks post study treatment. This takes into consideration the 14-day minimum interval between the sentinel subject and the second subject dosed in a cohort and the 4-week DLT observation period.

Related AEs Flag: AEs that are possibly, probably and definitely related to study treatment will be flagged as 'related' AEs. TEAEs with missing relationship will be considered as a related event. Relationship to ADVM-043 and Prednisone will be flagged separately.

Severity Flag: Subjects with the same TEAE and different severities will be flagged for the most intense severity. i.e., If the same event has been reported twice with severity 'Grade 1 – Mild' and 'Grade 3 – Severe' then the subject will be flagged as 'Grade 3 – Severe'. TEAEs that are missing severity will be presented in summary tables as 'Grade 3 – Severe'.

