7.0 ASSESSMENT OF SAFETY

The Investigator or site staff is to be responsible for detecting, documenting, and reporting all events that meet the definition of an AE or an SAE, regardless of relationship to ADVM-043 or their clinical significance.

For AEs and SAEs, the reporting period begins at the time a subject signs the informed consent and ends at 30 days after the last study visit. Between the time of informed consent and study treatment administration, only AEs (non serious and serious) assessed as related to study procedures should be reported. After treatment administration (Day 0), all AEs (serious and non serious, related and unrelated) should be reported.

Unless a subject withdraws consent for follow-up, each subject must be followed until a) the end of the AE reporting period at 30 days after the last study visit or
b) any ongoing drug-related AEs and SAEs have resolved or become stable. The Investigator should use appropriate judgment in ordering additional tests as necessary to monitor the resolution of events. The Adverum medical monitor may request that certain SAE/AEs be followed longer.

An SAE that is observed or reported prior to treatment administration and is associated with protocol-mandated interventions (eg, medication washout, bronchoscopy, or BAL) is to be recorded on the eCRF.

Any abnormal laboratory test result (hematology, chemistry, coagulation, or urinalysis) or other safety assessments (ECG, chest x-ray, vital sign measurements), is to be recorded as an AE or SAE. This includes those that worsen from Baseline and are clinically significant in the medical and scientific judgment of the Investigator,.

However, any clinically significant safety assessment that is associated with the underlying disease is not to be reported as an AE or SAE, unless judged by the Investigator to be more severe than expected for the subject's condition.

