7.1.2 Definition of Treatment-Emergent Adverse Event

A treatment-emergent adverse event (TEAE) is any event not present before exposure to the IMP or any event already present that worsens in either intensity or frequency after exposure to the IMP. The subject is to be instructed to contact the Investigator at any time after treatment administration if any symptoms develop.

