7.3 Reporting Adverse Events

All AEs reported or observed during the study are to be recorded on the AE eCRF. Information to be collected includes event term, time of onset; Investigator assessment of seriousness, severity, and relationship to ADVM-043; time of resolution of the event; any required treatment or evaluations; and outcome. An AE resulting from concurrent illnesses, reactions to concurrent

illnesses, reactions to concurrent medications, or progression of disease states must be reported. All AEs are to be followed to adequate resolution. The Medical Dictionary for Regulatory Activities (MedDRA) will be used to code all AEs.

Any medical condition that is present at the time that the subject is screened but does not deteriorate should not be recorded as an AE. However, if it deteriorates at any time during the study, it should be recorded as an AE.

Any SAE must be reported to [REDACTED] immediately; ie, within 24 hours after the time site personnel first learn about the event. The following contact information is to be used for SAE reporting:

[REDACTED]

Prompt notification of SAEs by the Investigator to Adverum [REDACTED] is essential so that legal and ethical responsibilities towards the safety of subjects are met.

Adverum [REDACTED] has a legal responsibility to notify both the local regulatory authority and other regulatory agencies about the safety of ADVM-043. Adverum [REDACTED] will comply with country-specific regulatory requirements relating to safety reporting to the regulatory authority, Institutional Review Board (IRB)/Independent Ethics Committee (IEC), and Investigators.

Investigator safety reports are prepared for suspected unexpected SAEs according to local regulatory requirements and Adverum [REDACTED] policy and are forwarded to Investigators as necessary.

Any Investigator who receives an Investigator safety report describing an SAE or other specific safety information (eg, summary or listing of SAEs) from Adverum [REDACTED] is to file it with the IRB and notify the IRB/IEC, if appropriate according to local requirements.

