7.3.1 Assessment of severity

The severity, or intensity, of an AE refers to the extent to which an AE affects the subject's daily activities. The intensity of the AE will be rated according to the Common Terminology Criteria for Adverse Events (CTCAE) version 4.0.

Grade 1: Mild; asymptomatic or mild symptoms; clinical or diagnostic observations only; intervention not indicated.

Grade 2: Moderate; minimal, local or noninvasive intervention indicated; limiting age-appropriate instrumental activity of daily living (preparing meals, shopping for groceries or clothes, using the telephone, managing money).

Grade 3: Severe or medically significant but not immediately life-threatening; hospitalization or prolongation of hospitalization indicated; disabling; limiting self-care activity of daily living (bathing, dressing and undressing, feeding self, using the toilet, taking medications, and not bedridden).

Grade 4: Life-threatening consequences; urgent intervention indicated.

Grade 5: Death related to AE.

Changes in the severity of an AE should be documented to allow an assessment of the duration of the event at each level of severity. AEs characterized as intermittent do not require documentation of onset and duration of each episode.

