6.10.1. Adverse Events

An AE is any untoward medical occurrence in an enrolled subject regardless of its causal relationship to the IMP. A treatment-emergent adverse event (TEAE) is any event that does not present before exposure to the IMP or any event already present that worsens in either intensity or frequency after exposure to the IMP.

A summary of TEAEs will include numbers and percentages of subjects with TEAE, DLT, ADVM-043-related TEAE, Prednisone-related TEAE, TEAE \geq grade 3, serious TEAE, treatment-related serious TEAE and Fatal TEAE.

AEs are to be coded using the Medical Dictionary for Regulatory Activities (MedDRA) (Version 20.1) classification to give a preferred term (PT) and system organ class (SOC) for each event.

In Mock Shell: Table 14.3.1.1

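### The SAP's start-date rule for flagging treatment-emergent AEs does not implement its own definition: it can miss a pre-dose AE that worsens after infusion, and it counts Day 0 AEs that began before the infusion

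*SAP*

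**What the plan says.** Protocol 7.1.2 gives the definition in two limbs. The first covers events that were absent before exposure. The second covers "any event already present that worsens in either intensity or frequency after exposure to the IMP". SAP 5.4.7 and SAP 6.10.1 carry the same two limbs.

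Under its TEAE flag entry, SAP 5.4.7 follows the definition with one operational sentence: "All AEs that started on/after Day 0 will be flagged as" treatment-emergent. No other flagging rule appears in either document. SAP 5.4 says that the conventions in that section govern the summaries.

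Four other provisions decide which events can be affected:

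- Between consent and dosing, Protocol 7.0 says that "only AEs (non serious and serious) assessed as related to study procedures should be reported". The same section names medication washout as a protocol-mandated intervention.
- For a condition present at screening, Protocol 7.3 says: "However, if it deteriorates at any time during the study, it should be recorded as an AE".
- Protocol 7.3.1 says: "Changes in the severity of an AE should be documented to allow an assessment of the duration" spent at each grade. It also waives episode-by-episode onset and duration for intermittent AEs.
- Protocol 7.3 lists time of onset among the items collected for each AE.

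On use of the flag, SAP 6.10.1 states: "A summary of TEAEs will include numbers and percentages of subjects with TEAE, DLT, ADVM-043-related TEAE", and continues with Grade 3 or higher, serious and fatal TEAEs. SAP 6.10.1.1 and 6.10.1.2 build the SOC/PT, related-TEAE and severity tables on TEAEs.

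**The concern.** The definition is anchored to exposure and has a worsening limb. The flag is anchored to a calendar day and has none. A programmer who applies the flag sentence as it stands will not produce the population that the definition describes.

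Safety is the primary objective, and the main safety tables are TEAE tables. An event that worsens after the vector is given is one that such tables exist to show. SAP 5.4.7 also has two cautious defaults, counting a missing relationship as related and a missing severity as Grade 3. Both are worded for TEAEs, so an event that loses the flag loses those protections as well. With 2 to 5 subjects per cohort, a single subject is a large share of any percentage.

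**Working it through.** The plan gives no figure to reproduce. The check is a comparison of the written definition with the date rule across the possible timing and recording patterns.

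| Pattern | TEAE by definition | Flagged by date rule | Agree? |
|---|---|---|---|
| New AE, starts after Day 0 | yes | yes | yes |
| Began before Day 0, does not worsen | no | no | yes |
| Began before Day 0, worsens after infusion, one record with the original start date | yes | no | **no** |
| Began before Day 0, worsening entered as a new record with a post-dose start date | yes | yes | yes |
| Starts on Day 0 before the infusion, does not worsen | no | yes | **no** |
| Starts on Day 0 before the infusion, worsens afterwards | yes | yes | yes |
| Starts on Day 0 after the infusion | yes | yes | yes |

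The two agree in five patterns and disagree in two.

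**Which events can fall in the third row.** Protocol 7.0 limits pre-dose AEs to those related to study procedures. Conditions present at screening that deteriorate become AEs under Protocol 7.3, and they are flagged if onset is dated at the deterioration. What remains is a procedure- or washout-related AE that began before Day 0, was still present at infusion, then worsened and was kept as one record. Such an AE is possible: subjects on augmentation therapy stop at least 8 weeks before dosing and stay off for at least 3 months after it, so a washout-related AE can span Day 0.

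**Whether a worsening gets its own record.** The documents do not say. Protocol 7.3.1 asks for severity changes to be documented. The severity flag in SAP 5.4.7 foresees the same event reported twice at different grades. For frequency, the waiver for intermittent AEs means that an increase need not generate a new onset date.

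**Which outputs depend on the flag.**

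- Dependent: any TEAE, related TEAE, TEAE of Grade 3 or higher, serious TEAE, and the SOC/PT and severity tables (SAP 6.10.1 to 6.10.1.2).
- Not dependent: the DLT flag, which SAP 5.4.7 defines on any AE that meets its criteria; the SAE tables of SAP 6.10.1.3, worded on SAEs; and the listing of all AEs in SAP 6.10.1.1.

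**Size per misclassified subject.** The change in a percentage is 100/n, if the subject has no other event in that row.

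- Cohort of 2: 100/2 = 50 points.
- Cohort of 5: 100/5 = 20 points.
- Total column: SAP section 6 excludes Cohort 4 and Part B. Assuming Cohorts 1 to 3 each hold 2 to 5 subjects, n is 6 to 15, so the change is 100/6 = 16.7 to 100/15 = 6.7 points.

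**The case against.** The best defence is that this is incomplete wording rather than an error. The date sentence says that all AEs from Day 0 are flagged, not that only those are, and the worsening limb stands just above it. If sites enter a worsening as a new record, the rule catches it. That stands in part: the documents leave the recording convention open. But no other rule implements the worsening limb, so the flag works only if an unstated convention is followed, and for frequency the protocol does not require that a new onset date exist.

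It can also be said that the Day 0 limb is trivial and errs on the cautious side. The pre-infusion procedures visible in Protocol 6.4.3.1 are vital signs and review of laboratory results (part is redacted), and only procedure-related events are collected then. This largely stands. A reader might infer that such events are attributed to the product. The documents do not support that, because relationship is assessed separately from treatment emergence.

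Third, the percentage shifts are just 100/n, and they vanish when the subject already has another event in the row. This stands and is built into the size given here.

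**Conclusion.** The flag rule departs from the definition it is meant to apply, in two patterns: a pre-Day 0 AE that worsens after infusion within one record, and a Day 0 AE that begins before infusion and does not worsen. The rule is wrong as written, though few events are likely to be touched. Where one is, and the subject has no other event in the row, a cohort percentage moves by 50 points at n=2 or 20 points at n=5.

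A reader might infer that worsened pre-dose AEs vanish from every TEAE table. The documents do not establish this, since it depends on a recording convention they leave open. A reader might also infer that DLT and SAE counts are built on the flag. They are not worded that way, and every AE is listed whether flagged or not. The flag is also not part of the escalation criteria: Protocol 3.7 rests these on review of safety data and DLTs.

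**What to change.** Replace the date sentence in SAP 5.4.7 with a rule along these lines: *an AE is a TEAE if its onset date and time are at or after the start of the ADVM-043 infusion, or if it began earlier and, after the start of infusion, its grade increased or the investigator judged its frequency to have increased. This applies whether the worsening is entered as a new record or as a severity change within the same record. A Day 0 onset with no recorded time is treated as a TEAE.*

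Add that the TEAE severity summaries use the post-infusion grade of a worsened event.

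The cost is a short SAP edit and a small programming change. Onset time and changes in severity are already to be collected. Frequency is the exception: it cannot always be derived from the data, so the investigator's judgement has to be obtained for the few AEs that were present before the infusion and continued after it.
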